The definitions of the Brazilian Ministry of Health (Brazil, 2020) will be used:

Flu syndrome (GS): Individual with acute respiratory condition, characterized by at least two (2) of the following signs and symptoms: fever (even if reported), chills, sore throat, headache, cough, runny nose, olfactory disorders or taste disorders.

Severe Acute Respiratory Syndrome (SARS): Individual with **GS** sit : dyspnea/respiratory distress OR persistent pressure in the chest OR O2 saturation less than 95% in room air OR bluish coloration of the lips or face.

Confirmed cases of COVID-19:

- **By clinical criterion:** Case of GSs or SRAG with clinical confirmation associated with anosmia (olfactory dysfunction) OR ageusia (gustatory dysfunction) acute without other previous cause.
- **Por clinical - epidemiological criterion:** Case of GSs or SRAG with a history of close or household contact, in the 14 days prior to the appearance of signs and symptoms with case confirmed for COVID-19.
- **By clinical criterion - imaging:** Case of GSS or SRAG or death from Rags that could not be confirmed by laboratory criterion And that presents at least one (1) of the following tomographic changes:
 - Peripheral, bilateral , **horizontal matte glass opacity** , with or without consolidation or visible intralobular lines ("paving"), **OR**
 - **Multifocal frosted glass** opacity of rounded morphology with or without consolidation or visible intralobular lines ("paving"),**OR**
 - **Reverse halo sign** or other findings of organizing pneumonia (later observed in the disease).
- **By laboratory criterion:** Case of SG or SRAG with test of:
 - **Molecular biology:** detectable result for SARS-CoV-2 performed by the RT-PCR method in real time.

- **Immunological:** reactive result for IgM, IgA and/or IgG performed by the following methods: Enzyme-Linked Immunosorbent Assay (ELISA); Immunochromatography (rapid test) for antibody detection; Electrochemiluminescence Immunoassay (ECLIA);

- **Antigen Research:** reagent result for SARS-CoV-2 by immunochromatography method for antigen detection.

- **By laboratory criterion in asymptomatic individual:** Asymptomatic individual with test results:

- **Molecular Biology:** detectable result for SARS-CoV-2 performed by the RT-PCR method in real time;

- **Immunological:** reagent result for IgM and/or IgA performed by the following methods: ELISA or Immunochromatography (rapid test) for antibody detection.

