Health professionals from other institutions besides those participating in the study may participate in the research. In this case, they will contact the participating centers, through telephone contact or email, informing their interest. All follow-up of these participants will be carried out by the center in which the subject was recruited.

The first evaluation (*Screening* or recruitment) of the study can be initiated in person or through telephone contact, email or electronic media. If the eligibility criteria are met, the individual will be invited to attend the study center for the signing of the Informed Consent and collection of exams that will confirm his or her eligibility or not.

Over four other face-to-face visits [M0 or inclusion, M1 (10 days after the intervention), M3 (90 days after the intervention) and M6 (180 days after the intervention)] the *status* of Coronavirus infection will be monitored by real-time PCR, in the case of symptomatic, and coronavirus serology every 3 months after vaccination with BCG or placebo (chart below). The tests will be performed with the purpose of having the diagnosis of the infection either through the real-time polymerase chain reaction (RT-PCR) technique and/or through the qualitative identification of IgM+IgA and/or IgG antibodies in the detection of infections that occurred asymptotically and that may have been attenuated by the intervention with the BCG vaccine. For individuals receiving specific immunization against SARS CoV 2, serology will not be used for diagnosis of asymptomatic infection.

At the time of recruitment hiv serology and BHCG dosage will also be collected for *women with status* in order to meet the eligibility criteria. The time between the examinations collected in the recruitment and the effective inclusion in the study should be up to 10 calendar days. If the return occurs between the third and tenth day, and the

participant presents symptoms compatible with COVID-19 upon return, the participant should recollect the RT-PCR.

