The gamma interferon release assay (IGRA) will preferably be performed at the inclusion visit or M0 for the purpose of identifying *patients previously infected with Mycobacterium tuberculosis* and detecting gamma interferon (IFN) levels, as well as its role in preventing viral infection, despite knowledge about alpha and beta INFs in immunopathogeny against the virus. In case of non-conformities that make the quality in the performance of this test, in view of being an examination that requires technical details crucial for its performance, the participant will be invited to perform a recollection. In case of participants with previous IGRA reagent and who prove through the exam report will not be submitted to the new collection for this purpose. The other tests will be useful in evaluating the inflammatory response of individuals vaccinated and not vaccinated with BCG and those who became ill or not by COVID-19.

If RT-PCR tests for nasoarcheal swab coronavirus, coronavirus serology and/or HIV serology performed during recruitment, generate inconclusive or indeterminate results, participants will be invited to a new collection and confirmation of the result. Participants will only be included with certain negative or non-reagent results for the three tests, with the exception of cases that have received vaccines against COVID-19, when serology will not be used as a determinant for inclusion or not. In case of participants who present reagent results in hiv serology, they will be referred to the Infectious Diseases service of the study centers for evaluation and follow-up.

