Participants who present some test results collected during the study outside the normal range will be evaluated by the study physician. It should be indicated in the participant's folder that this result has been verified and whether or not there is clinical significance. If any, the participant should be referred for specialist evaluation at the hospital where his follow-up is being carried out.

Visits	Evaluations	Exams	Procedures
Screening or Recruitment	Face-to-face assessment of eligibility criteria, application of the TCLE	NASOarchyeal swab RT-PCR, anti-SARS-Cov-2 antibody levels, BHCG dosage and HIV serology	Invitation to participate in the study, application of the TCLE, collection of clinical samples (nasopharangeal swab and blood).
Inclusion or M0 0 day of preventive treatment (ToT) (BCG or placebo)	Face-to-face assessment with confirmation of eligibility, clinical inclusion visit, collection of exams and dose of BCG or placebo	IGRA; Complete blood count, lipidogram, albumin, HbGlic, LDH, PCR, ESR, D-D-Dmer; and biomarkers*.	Nursing and medical consultation. Collection of clinical sample (blood). Application of preventive treatment.
S1 - S12 7-90 days of preventive TTO (±3 days)	Telephone and/or SMS contact, and/or weekly email and sending photo of the injection site	No exams	Fever questionnaires and/or respiratory signs and symptoms and photo submission of the injection site
M1 10 days of preventive TTO (±5 days)	Face-to-face visit to the laboratory for blood collection for biomarkers	Anti-Anti-SARS-Cov-2 antibody levels; Complete blood count, lipidogram, albumin, HbGlic, LDH, PCR, ESR, D-D-Dmer; and biomarkers*.	Collection of clinical sample (blood).
M3 90 days of preventive TTO (±14 days)	Face-to-face clinical visit for follow-up and blood collection for serology	Anti-Anti-SARS-Cov-2 antibody levels	Nursing and/or medical consultation. Collection of clinical sample (blood).
M4/M5 120/150 days of preventive Tom (±14 days)	Telephone contact and/or SMS, and/or weekly email	No exams	Fever questionnaires and/or respiratory signs and symptoms
M6 180 days of preventive TTO (±14 days)	Face-to-face clinical visit to close the study and for blood collection for serology	Anti-Antibody levels anti-SARS-Cov-2.	Nursing consultation. Collection of clinical sample (blood).
Fever and/or respiratory signs and symptoms	Face-to-face visit to the Worker's Health sector of its study center to collect exams	RT-PCR	Clinical sample collection (swab and blood).

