Conventional examinations will be called those performed by the Clinical Pathology laboratories contracted for the purpose of the study.

These are: blood count, hemosedimentation velocity (ESR), lactate dehydrogenase (LDH), total cholesterol and fractions and triglycerides, D-dummer, C-reactive protein (CRP), albumin, ferritin, iron, glycated hemoglobin. For this purpose, 1 EDTA tube – purple cap and 1 serum tube (red cap) should be delivered for laboratory analysis.

Polymerase chain reaction with real-time reverse transcription:

The presence of SARS-CoV-2 in respiratory samples will be detected by real-time amplification by RT-PCR from the open reading chart SARS-CoV-2 1ab (ORF1ab), nucleocapsid protein (NP) gene fragments using kits provided by IDT USA. The conditions

for amplifications will be 50 °C for 15 minutes, 95 °C for 3 minutes, followed by 45 cycles of 95 °C for 15 if 60 °C for 30 s. When two targets (ORF1ab, NP) test positive by specific real-time RT-PCR, the case will be considered laboratory confirmed. A cycle threshold value (Ct value) less than 37 will be defined as a positive test and a Ct value of 40 or more has been defined as a negative test. An average load, defined as a Ct value of 37 to less than 40, will require confirmation per new test.

Serological test for COVID-19

The Vircell serological test will be® used to define the inclusion or not of health professionals in the study. Vircell reveals® the presence of IgG and IgM/IgA against viral antigens as well as their titration, facilitating the monitoring of absolute antibody values.

Immunoassays

Seros will be obtained from the health professionals enrolled in the study. Two cohorts will be considered: health professionals vaccinated with BCG (n=376) and health professionals not vaccinated with BCG (n=376).

The biomarkers evaluated will be cit-H3, alpha 1 AT, D-dummer, LDH and PCR. The analyzed data will be related to the blood count information, according to the scheme: M0, M1, M3 and M12.

Inflammatory profile and population characterization of neutrophils and T lymphocytes

A panel of surface and intracellular markers more related to exacerbated inflammation will be used, aiming to study the profile of T lymphocytes, monocytes and neutrophils.

Cell profiles will be compared to the occurrence or not of SARS-CoV-2 infection in both cohorts.

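### Primary outcome 1 has two conflicting serology rules for asymptomatic infection, one without IgG and one with it, and the analysis plan does not choose between them

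*Combined protocol and SAP*

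**What the plan says.** Study Definitions (under Methodology) adopts the Ministry of Health case definitions. For a person without symptoms it accepts a detectable RT-PCR, or a "reagent result for IgM and/or IgA performed by the following methods: ELISA or Immunochromatography (rapid test) for antibody detection". The same section does list IgG for people with symptoms, so IgG is missing only from the asymptomatic rule.

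Study visits takes a different line. It introduces the follow-up tests with "The tests will be performed with the purpose of having the diagnosis of the infection" and then names, beside RT-PCR, the "qualitative identification of IgM+IgA and/or IgG antibodies in the detection of infections that occurred asymptotically" (the last word evidently means without symptoms). Infection status after the intervention is "monitored by real-time PCR, in the case of symptomatic, and coronavirus serology every 3 months after vaccination with BCG or placebo".

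Other relevant text:

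- On entry, Study visits says "Participants will only be included with certain negative or non-reagent results for the three tests": RT-PCR, coronavirus serology and HIV serology. The exception is people already vaccinated against COVID-19, for whom serology does not decide entry.
- The assay section (Serological test for COVID-19) says the kit shows "the presence of IgG and IgM/IgA against viral antigens as well as their titration", so the antibody classes can be told apart.
- Secondary Objectives and Study visits both rule out serology for diagnosing asymptomatic infection in participants vaccinated against COVID-19.
- The Statistical Analysis Plan bases the primary analysis on COVID-19 diagnostic tests together with hospital data and national notification systems. It names no antibody class, case rule or visit. The Outcomes section does not define infection either.

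**The concern.** A participant without a COVID-19 vaccine who enters seronegative, has no symptoms, and is reactive for IgG alone at M3 or M6 is infected according to Study visits and is not a case according to Study Definitions. Both rules cannot be followed.

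This reaches the primary outcome because follow-up RT-PCR is for symptomatic participants. Scheduled trial serology is therefore the main planned route to an asymptomatic infection. Study visits says this testing is meant to find infections that BCG may have attenuated, and the IgM/IgA-only rule would discard some of them.

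The same undefined outcome feeds the interim analysis. If the rule stays open, it could be settled after data have been seen.

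**Working it through.** **The texts side by side, for a participant with no symptoms and no COVID-19 vaccine**

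| Result at M3 or M6 | Study Definitions | Study visits |
|---|---|---|
| RT-PCR detectable (not scheduled without symptoms) | case | case |
| IgM and/or IgA reactive | case | case |
| IgG reactive only | not a case | case |

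Only the last row differs. Nothing in the Statistical Analysis Plan, Outcomes or Interim Analysis Plan settles it.

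**The plan's own expected counts** (Outcomes, item 3; 376 per arm, 80% vaccinated against COVID-19)

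- BCG only: 376 × 0.20 × 0.20 = 15.04 (plan: 15)
- Neither vaccine: 376 × 0.20 × 0.30 = 22.56 (plan: 23)
- COVID-19 vaccine only: 376 × 0.80 × 0.15 = 45.12 (plan: 45)
- Both: 376 × 0.80 × 0.15 × 0.85 = 38.35 (plan: 38)

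These reproduce. The placebo arm expects 23 + 45 = 68 infections and the BCG arm 15 + 38 = 53, so 121 in all. Of these, 15 + 23 = 38 are in participants without a COVID-19 vaccine, the only group in which serology can make a case.

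**Size of the conflict.** The documents do not give the share of infections that are asymptomatic or, of those, the share reactive for IgG only at sampling. I assume 20-50% and 25-75%, equal in both arms, and assume that the plan's counts include IgG-only cases.

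- Share of the 38 affected: 0.20 × 0.25 = 0.05, to 0.50 × 0.75 = 0.375
- Events lost under the IgM/IgA-only rule: 38 × 0.05 = 1.9, to 38 × 0.375 = 14.25 (1.6% to 11.8% of 121)
- Placebo: 23 × 0.05 = 1.15, to 23 × 0.375 = 8.6
- BCG: 15 × 0.05 = 0.75, to 15 × 0.375 = 5.6

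Power uses the two-sided 5% normal approximation for two proportions with n = 376 per arm:

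Φ{ [ |p1 − p2|√n − 1.96√(2p̄(1 − p̄)) ] / √(p1(1 − p1) + p2(1 − p2)) }

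| Rule and assumption | Placebo | BCG | Risk ratio | Power |
|---|---|---|---|---|
| IgG counted | 68 | 53 | 53/68 = 0.779 | 31.8% |
| IgG not counted, 5% affected | 66.85 | 52.25 | 0.782 | 30.8% |
| IgG not counted, 37.5% affected | 59.4 | 47.4 | 0.798 | 24.0% |

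The ratio moves slightly toward 1 because the lost events come from the group where the plan expects the larger BCG effect (15/23 = 0.65, against 38/45 = 0.84 with a COVID-19 vaccine). The rule itself treats the arms alike.

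**M1.** Serology is also drawn at M1, on day 10 plus or minus 5. On the screening sample the plan says "The time between the examinations collected in the recruitment and the effective inclusion in the study should be up to 10 calendar days". The two samples are thus 0 + 5 = 5 to 10 + 15 = 25 days apart, and a conversion at M1 may reflect infection acquired around screening.

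**The case against.** The strongest reply is that Study Definitions governs. It is labelled as the place for definitions and says the Ministry's will be used. The analysis plan draws partly on national notification data, and the Ministry source in the reference list concerns case definition and notification, so notified cases plausibly follow the IgM/IgA rule. Study visits, on this view, only explains why tests are done. This has weight but does not close the matter. Study Definitions defines confirmed COVID-19 cases, while the outcome is SARS-CoV-2 infection, the notion that Study visits uses. If the two terms mean the same, the rules conflict. If they differ, the plan never says which one the outcome follows. Either way the analyst has to choose.

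The opposing case is right on several stronger readings that a reader might infer:

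- *That trial serology is the only route to an asymptomatic case.* It is not. Hospital and notification data could supply a positive test made elsewhere. How often is unknown.
- *That M1 conversions are wholly unaddressed or meant to count.* Secondary Objectives names M3 and M6, Study visits says every three months, and the visit table describes the M1 blood draw as being for biomarkers but those at M3 and M6 as being for serology. All three point away from M1. What is missing is one explicit line.
- *That conversions on samples drawn before a first COVID-19 vaccine dose are thrown away.* The exclusion carries no date, but its stated reason is bias from vaccine use, which suggests that later samples were meant. This is too speculative to press.

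The reply is also right that including IgG departs from the Ministry definition, and that one rule for asymptomatic infection leaves open whether the clinical, epidemiological and imaging criteria count toward outcome 1.

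**Conclusion.** The conflict is real and rests on the text alone: an IgG-only conversion is or is not a primary event depending on the section followed. Its reach is narrow. It is limited to participants without a COVID-19 vaccine, 38 of the 121 expected infections. Under the assumed shares it costs about 2 to 14 events, moves the expected risk ratio from 0.78 to at most 0.80, and lowers power at the plan's own counts from about 32% to between 31% and 24%. The larger loss needs both upper limits together.

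A reader might infer that the choice of rule biases the comparison. The documents do not support that. Each rule applies identically in both arms, and no figure suggests that the IgG-only share differs between them. The effect is on event count and precision, not direction. Nor should the 32% starting power be charged to this point: it comes from the expected counts in Outcomes, item 3, and is a separate sample-size question.

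Severity: minor to moderate.

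**What to change.** State one rule in Study Definitions, Study visits and the Statistical Analysis Plan. For participants without a COVID-19 vaccine, asymptomatic infection is a positive RT-PCR, or IgG and/or IgM/IgA seroconversion at M3 or M6 from the non-reactive baseline already required for entry. Including IgG fits sampling three months apart and the stated aim of finding attenuated infections.

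Add one line saying that a conversion at M1 is not counted in the main analysis, with a sensitivity analysis that includes it. Report the IgM/IgA-only rule as a second sensitivity analysis, so that results under the Ministry definition can also be seen.

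The cost is wording and a little extra analysis. The assay already reports both antibody results, and the samples are already scheduled. The downside is a departure from the Ministry definition for IgG-only cases, which the text should acknowledge.

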From the first case to the present day, the COVID-19 epidemic has been identified in 185 countries, with the notification of 2,666,154 cases and 186,144 deaths (Source: COVID Visualizer, 23Apr2020). In Brazil, more than 45,757 cases and 2,906 confirmed deaths by COVID-19 have been confirmed (Source: COVID Visualizer, 23Abr2020). In our country, to date, testing for COVID-19 occurs only in severe cases and few centers offer the service to health professionals, a population at high risk of infection. Thus, the data in Brazil present a high of underreporting. According to the UFRJ Technical Note, it is estimated that the cases reported in Brazil represent approximately only 11% of the cases (Kritski *et al*, 2020).

It is known that the impact of the disease differs between countries. These differences are attributed to the different cultural norms, mitigation efforts, available health infrastructure and socio-economic level. Recently, Miller *et al* (2020) proposed, through an ecological study, that countries that continued with the use of *vaccination with Bacillus Calmette Guérin* (BCG) after birth have a lower occurrence of COVID-19.

BCG is a vaccine produced from a live attenuated strain derived from an isolate of *Mycobacterium bovis* and is widely used worldwide as a tuberculosis (TB) vaccine, and countries such as Portugal, Japan and China adopt a universal BCG vaccination policy in newborns. Other countries such as Italy, the Netherlands, Spain, France, Switzerland and the United States of America have discontinued or have not adopted universal vaccination policies due to the low risk, when compared to countries with high prevalence of the disease, of developing *Mycobacterium tuberculosis* (MTB) infections, and also due to the variable efficacy in the prevention of tuberculosis in adults (Miller *et al*, 2020).

Interestingly, shortly after its introduction in the 1920s, epidemiological studies showed that the BCG vaccine reduced infant mortality regardless of its effect on TB (reviewed by Shan *et al*, 2009). In several observational studies in West Africa, there was a 50% reduction in the overall mortality of children vaccinated with BCG, an effect too large to be explained by the protection against tuberculosis only (Garly *et al*, 2003; Roth *et al*, 2005). More recently, these findings have been validated in controlled trials (Aaby *et al*,

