- **Health Professional:** For the purposes of this study, in addition to the definition of a health professional established in Resolution 218 - 97 - Regulation of health professions, the Brazilian Classification of Occupations will be used, and in an expanded way will be included undergraduate students in the area of health sciences who attend the hospital and are in direct contact with patients. Administrative technical professionals who circulate or perform activities in sectors within the hospitals participating in the study and who have direct contact with patients may also be included in the study, such as receptionists, maqueiros, security guards, among others.

Study Design:

The project proposes to monitor research participants for 6 months and thus conduct a controlled clinical trial, phase II-B, which compares the occurrence of SARS-CoV-2 infection as well as the time to infection among health professionals receiving bcg vaccine (experimental group) compared to those receiving placebo (control group). Coupled with the clinical trial, participants will also be analyzed in an observational study of two cohorts of volunteers, vaccinated with BCG and not vaccinated. In this part of the

study, participants will be analyzed in relation to the inflammatory profile, considering biomarkers predicting infection and evolution to severe form of COVID-19.

Study site:

The possible participants of this research will be recruited in two hospitals in the city of Rio de Janeiro (Hospital Complex Institute of Chest Diseases - Clementino Fraga Filho University Hospital of UFRJ and Pedro Ernesto University Hospital Complex - Piquet Carneiro Polyclinic of UERJ) and a hospital in the city of Barueri in SP (Hospital Municipal [name] - Barueri/SP).

Eligibility criteria:

Health professionals (according to the definitions of this study), who are in the exercise of their activities in the units of the study or not, of both sexes over the age of 18 years and who agree to participate in the study by signing the Informed Consent Form (TCLE).

Inclusion criteria:

1. Individuals aged 18 ≥, male or female, not infected with SARS-CoV-2
2. Agreement to participate in the study by signing the TCLE
3. Not being pregnant in case of women able to become pregnant

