4. Have not received a specific vaccine against COVID-19 or, if vaccinated against SARS-CoV-2, have received the complete immunization schedule only with vaccines approved by ANVISA and implemented by the National Immunization Program, (including the second dose) within a minimum of 15 days prior to the date of inclusion in the study
5. If the participant have not received a specific vaccine against COVID-19 approved by ANVISA, be aware and agree to be able to receive them only 15 days after the intervention proposed in this study

Exclusion criteria:

1. Professionals with a history of sars-cov-2 confirmed infection through RT-PCR or who have already presented clinical and molecular diagnosis of COVID-19 prior to the study

2. Individuals who have not undergone confirmatory tests for COVID-19
3. Breastfeeding
4. Individuals who report having primary or acquired immunodeficiency
5. Individuals who report being affected by malignant neoplasms
6. Patients reporting treatment with high-dose corticosteroids (equivalent to the prednisone dose of 20 mg/day or more) for more than two weeks
7. Patients who report being on other immunosuppressive therapies (antineoplastic chemotherapy, radiotherapy, among others)
8. Individuals who report being diagnosed with autoimmune diseases
9. Dermatological conditions at the vaccine site or generalized
10. Individuals who report being treated for active tuberculosis
11. Individuals who report a history of previous treated tuberculosis
12. Individuals with febrile symptoms (body temperature $\geq 37.5^{\circ}\text{C}$ in the last 48h)
13. Participation in other clinical prevention trials for COVID-19 (vaccines already approved by ANVISA for use by the National Immunization Program are not included in this item)
14. Report of vaccination with live microorganism administered in the month prior to randomization
15. Require that, if another vaccination with live microorganism is required, it is administered in the month following randomisation (If the other live vaccine can be administered on the same day, this exclusion criterion does not apply)
16. Known anaphylactic reaction to any ingredient in bcg vaccine
17. Adverse reaction prior to BCG vaccine [significant local reaction (abscess) or suppurative lymphadenitis]
18. BCG vaccine administered in the last year

Intervention Plan:

Intervention:

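### Exclusion criterion 1 recognises only molecular proof of past infection; with entry serology waived for people already COVID-vaccinated, antigen- or antibody-proven past infection can enter unrecorded, mainly in that group

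*Combined protocol and SAP*

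**What the plan says.** All references are to the combined protocol and SAP.

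- **Exclusion criteria, item 1** removes "Professionals with a history of sars-cov-2 confirmed infection through RT-PCR or who have already presented clinical and molecular diagnosis of COVID-19 prior to the study". Antigen and antibody results are not mentioned.
- **Inclusion criteria, item 1** asks for adults, "male or female, not infected with SARS-CoV-2". It gives no time frame and names no test.
- **Study Definitions** accept more than RT-PCR as laboratory confirmation. In a symptomatic case, a "reactive result for IgM, IgA and/or IgG performed by the following methods" counts, as does a "reagent result for SARS-CoV-2 by immunochromatography method for antigen detection". In an asymptomatic person, reactive IgM or IgA counts.
- **Study visits** sets the entry tests (RT-PCR, SARS-CoV-2 serology, HIV serology): "Participants will only be included with certain negative or non-reagent results for the three tests", but "with the exception of cases that have received vaccines against COVID-19, when serology will not be used as a determinant for inclusion or not".
- **Inclusion criteria, items 4 and 5** admit people fully vaccinated at least 15 days before inclusion. They also admit unvaccinated people, who agree to wait 15 days after the intervention before a COVID-19 vaccine.
- **Sample size** assumes that 80% of the cohort is COVID-vaccinated. **Outcomes, item 3** plans to find predictive biomarkers by comparing infected with uninfected professionals. **Secondary Objectives 13 to 15** add biomarkers, a predictive model and risk factors. Past infection is not among the factors that objective 15 lists.

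**The concern.** The protocol uses one standard of proof for what counts as COVID-19 and a narrower one for who has already had it. Entry serology partly makes up the difference in unvaccinated candidates. In people vaccinated before entry nothing does, because their serology does not decide inclusion and exclusion 1 does not ask about antigen or antibody results.

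Two things follow. First, some partly immune people join the denominator and lower the event rate. Second, past infection becomes an unrecorded cause of remaining uninfected. Analyses that contrast infected with uninfected participants are not protected by randomisation. Previously infected people would gather on the uninfected side, so a marker of past infection could be taken for a marker of protection. Screening for past infection also differs between people vaccinated before entry and people vaccinated after it, which complicates any reading across COVID-vaccine categories.

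**Working it through.** **1. Who passes, by candidate type.** Each has a documented past positive antigen or antibody test, no past RT-PCR proof, and a negative RT-PCR at screening.

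| Candidate | Exclusion 1 | Serology at recruitment | Result |
|---|---|---|---|
| COVID-vaccinated before entry | not met | does not decide | no named bar |
| Unvaccinated, reactive | not met | bars entry | excluded |
| Unvaccinated, non-reactive | not met | passes | no named bar |

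Inclusion 1 could be read as barring the first and third rows, but it does not say whether past infection counts or how it is shown.

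**2. The plan's expected infections (Outcomes, item 3).** With 376 per arm and 80% COVID-vaccinated, each arm has 300.8 vaccinated and 75.2 unvaccinated.
- BCG only: 75.2 × 0.20 = 15
- Neither vaccine: 75.2 × 0.30 = 23
- COVID-19 vaccine only: 300.8 × 0.15 = 45
- Both: 300.8 × 0.15 × 0.85 = 38

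All four match the plan. The COVID-vaccinated participants contribute 45 + 38 = 83 infections.

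**3. Effect on events.** The documents give neither the frequency of such histories nor the protection they confer. Assume that a fraction f = 5-20% of COVID-vaccinated participants have one, and that it lowers their risk by r = 60-80%. The risk in this group is multiplied by m = 1 − f × r.
- Low: m = 1 − 0.05 × 0.6 = 0.97. The 15% becomes 14.6%, and 83 × 0.03 = 2.5 infections are lost.
- High: m = 1 − 0.20 × 0.8 = 0.84. The 15% becomes 12.6%, and 83 × 0.16 = 13.3 infections are lost.

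This applies f to everyone in the 80%, including people vaccinated after entry who had passed serology. If half were vaccinated after entry (an assumption) and had no such history, the loss halves to about 1 to 7.

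**4. Effect on power.** The plan's mixed rates are:
- placebo: 0.2 × 0.30 + 0.8 × 0.15 × m
- BCG: 0.2 × 0.20 + 0.8 × 0.15 × 0.85 × m

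Two-sided 5% is assumed, since sidedness is not stated. Power = Φ[(d − 1.96·se0)/se1], where d is the difference in rates, se0 uses the pooled rate, se1 the separate rates, and n = 376 per arm. At m = 1: d = 0.038, se0 = 0.02681, se1 = 0.02677, giving Φ(−0.543) = 29.4%.

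| m | Placebo | BCG | Power |
|---|---|---|---|
| 1.00 | 18.0% | 14.2% | 29.4% |
| 0.97 | 17.6% | 13.9% | 29.1% |
| 0.84 | 16.1% | 12.6% | 27.9% |

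The loss is 0.3 to 1.5 points. With f = 40% and r = 80% (m = 0.68) the rates are 14.2% and 10.9% and power is 26.6%, a loss of 2.8 points. The low starting power comes from the plan's own mixed rates, not from this gap.

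**5. Effect on the infected-versus-uninfected contrast.** Take COVID-vaccinated participants without BCG, with a 15% risk if never infected. The share with past infection is f(1 − r)/(1 − fr) among the infected and f[1 − 0.15(1 − r)]/[1 − 0.15(1 − fr)] among the uninfected.
- Low: 0.05 × 0.4/0.97 = 2.1% against 0.05 × 0.94/0.8545 = 5.5%.
- High: 0.20 × 0.2/0.84 = 4.8% against 0.20 × 0.97/0.874 = 22.2%.

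On the same assumptions that barely move power, past infection is roughly 2.7 to 4.7 times as common among the uninfected.

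**The case against.** The case for leaving the text alone has real force.

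- **Inclusion 1 may already cover it.** Read with the Study Definitions, the requirement to be uninfected could bar antigen-proven people. That stands as far as it goes: the text is ambiguous rather than clearly permissive. Sites could still apply it differently.
- **Waiving serology is deliberate.** The protocol explains, for endpoints, that COVID-19 vaccination distorts serology, and RT-PCR is still required at entry. This also stands. The waiver is reasonable; what is missing is a question about earlier test results to take its place.
- **The affected group is narrow.** It needs documented antigen or antibody proof without RT-PCR proof. The Introduction says that testing was then limited to severe cases, with few centres testing professionals. That describes April 2020 and may have changed, but it gives no support for the upper end of the assumed range.

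A reader might infer that "it is estimated that the cases reported in Brazil represent approximately only 11% of the cases" shows a large pool of such entrants. It does not. That figure concerns unreported infection, which an eligibility line about documented tests cannot reach.

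A reader might also infer that the SAP tests COVID-vaccinated against unvaccinated participants and that this test is confounded. The Statistical Analysis Plan names BCG versus placebo, by infection status, within vaccine categories. Since COVID vaccination is not randomised, a contrast across categories would be confounded in any case.

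**Conclusion.** The gap is real and minor. Exclusion 1 is narrower than the protocol's own laboratory definitions, and no deciding test covers the difference in people vaccinated before entry.

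Three stronger readings are tempting, and the documents do not support them:
- **That the gap exists only among the COVID-vaccinated.** Unvaccinated people who are non-reactive at recruitment pass as well. It lies mainly, not solely, in the vaccinated group.
- **That the waiver covers 80% of participants.** The 80% is the share vaccinated in the cohort. Recruitment is scheduled from 30/10/2020, COVID-19 vaccines were approved for emergency use in January 2021, and vaccination after entry is allowed. The share vaccinated before entry is not stated, so 83 affected events and 2 to 13 lost are upper bounds for the assumed ranges.
- **That the primary comparison is biased.** Allocation is randomised 1:1, so past infection is balanced between arms on average.

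The cost in power is at most about 1.5 points under 5-20% past infection and 60-80% protection. What matters more is interpretation: the infected-versus-uninfected biomarker and predictive analyses, and any reading across COVID-vaccine categories, cannot separate documented past infection from the factors studied unless it is recorded.

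**What to change.** 1. Reconcile inclusion 1, exclusion 1, the Study Definitions and the entry-test rule in Study visits. Past infection confirmed by any of the protocol's laboratory criteria should be treated the same way in every candidate. An antibody result should count only if dated before the first COVID-19 vaccine dose.
2. Add one screening question on earlier RT-PCR, antigen and antibody results with dates. Collect the same information retrospectively from those already enrolled. Antibody levels taken at recruitment are not a substitute in vaccinated people, because they may not separate past infection from vaccine response.
3. Use recorded past infection as a covariate in the biomarker and predictive analyses (Outcomes, item 3; Secondary Objectives 13 to 15).
4. Repeat the primary analysis without these participants as a sensitivity analysis. The history precedes randomisation, so removing them does not break the randomised comparison, provided that it is established without knowledge of the allocated arm.

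The Schedule shows an amendment submission in August 2021 and recruitment to 31/12/2021, so the change could go with that submission. The cost is one aligned eligibility line, one question, and a slightly smaller pool of candidates. Undiagnosed past infection remains and should be stated as a limitation.
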